4. Is the event rate different for those previous users of aspirin who were not randomised to it compared to previous users who continued with aspirin as their randomised treatment?
5. Investigation of the hypothesis that aspirin will have a chemopreventive effect on all epithelial cancers using the same mechanism it does to reduce oesophageal cancer, however, high dose PPI therapy may arguably increase colon cancer incidence as gastrin levels increase and this hormone is a known stimulant for colon cancer in mice.
6. Look for a dose/time response effect for aspirin and for esomeprazole.

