NOTE on retrospective patients. It is acceptable for primary outcome investigation not to be linked to date of randomisation since we will be using the actual time of an event. Events linked to endoscopy may occur at screenings or during an endoscopy for change of symptoms. Follow-up forms will be completed at yearly intervals from randomisation and QOL forms posted out at 2 yearly intervals from randomisation (for relevant patients).

At each endoscopy any macroscopic abnormality of the Barrett's metaplasia will be biopsied as per local practice and samples taken for formalin fixation and local histological assessment for dysplasia. DNA and RNA will be extracted from the paraffin embedded material for SNP analysis and micro array analysis. In addition an extra biopsy will be taken at each level and snap frozen for genetic studies. In addition to the endoscopy, blood samples will be taken at baseline, between 4 and 6 years, 8 years and at 10 years if the patient consented to extended follow-up, to assess cardiovascular risk factors and the remainder stored for analysis of circulating genetic mutations as and when reliable assays become available.

Patients will come to the hospital pharmacy every 6 months to drop off unused medication and pick up a new 6 month supply.

AspECT

A phase III randomised study of Aspirin and Esomeprazole chemoprevention in Barrett's metaplasia

Funded by CR-UK, MRC, UHL and NCI

ISRCTN No.85156844

The factorial design is efficient due to each patient contributing to the answer to 2 questions. Not only must it be possible for patients to receive both treatments (practically and with consideration of toxicity) but the anticipated treatment effects must be approximately additive. The patients taking part in the PPI only randomisation will be analysed for the PPI primary aim but will not be available for the aspirin primary aim.

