ANALYSIS: Using the survival time calculated for the primary objective, a logrank test to assess the effect of gender with both males and females in the sample will be reported in a table as for the primary objective. Create an AFT model looking at the gender effect adjusting for age, length of Barrett's and presence of intestinal metaplasia so that there is a time ratio with 95% confidence interval for the gender effect. Repeat with a Cox model if assumptions valid. Redo both of these models with treatment also included.

Exploratory aim

To assess aspirin's role on the development of colorectal adenomas and cancer

Use as outcome the time to colorectal cancer or colorectal adenoma. Using a logrank test, consider if aspirin use is prognostic.

To collect and bank samples for use in future ethically approved studies

To be analysed under other protocols and analysis plans.

And the exploratory uses of the data

- Describe Barrett's length over repeat biopsies and investigate a change in length from baseline to 2 years between treatment groups.

ANALYSIS: For all patients, assess if Barrett's metaplasia length shows a trend with time using repeated measures anova.

Using the baseline and 2 year length, compare the Barrett's length difference between treatment groups using paired ttest.

- Can intervention with aspirin result in a lower stage of adenocarcinoma ?
Can intervention with PPI result in a lower stage of adenocarcinoma ?

ANALYSIS: Chi square trend test on the following tables

AspECT

A phase III randomised study of Aspirin and Esomeprazole chemoprevention in Barrett's metaplasia

Funded by CR-UK, MRC, UHL and NCI

ISRCTN No.85156844

	No aspirin	Aspirin
None		
Stage I		
Stage II		
Stage III		
Stage IV		

	Low PPI	High PPI
None		
Stage I		
Stage II		
Stage III		
Stage IV		

Note: this ignores the different follow-up times

- Does adjustment for oesophagectomy, ablation therapy, endoscopic mucosal resection change the treatment effect ?

ANALYSIS: Within the multivariate AFT and COX models, add time dependent variables for the above and note the new treatment effect.

- Is the event rate different for those previous users of aspirin who were not randomised to it compared to previous users who continued with aspirin as their randomised treatment?

ANALYSIS: Kaplan-Meier curve and Logrank of the previous users of aspirin who were not randomised to it versus those randomised to aspirin.

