- Investigation of the hypothesis that aspirin will have a chemopreventive effect on all epithelial cancers using the same mechanism it does to reduce oesophageal cancer, however, high dose PPI therapy may arguably increase colon cancer incidence as gastrin levels increase and this hormone is a known stimulant for colon cancer

ANALYSIS: Define outcome as time to epithelial cancer (oesophageal, colorectal, other gi or skin). For those randomised to aspirin and low PPI or to no aspirin and low PPI, use an AFT model with stratification variables to assess if aspirin is predicting outcome.

Where possible, all these analyses will use the ITT sample.

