9.1 Resource Use and Cost Data

The health economics data for this trial will not be analysed by CSM; the analysis will be undertaken by [name].

10. Exploratory analyses not specified prior to receiving data

Any analyses not specified in this document will be exploratory in nature.

11. Serious adverse events

Serious adverse events are defined as those that are fatal, life threatening, disabling, a congenital birth defect, another important medical event which require hospitalisation or prolongation of hospitalisation. Any serious adverse event occurring whilst a participant is continuing in the study, until trial medication is stopped will be recorded. All serious adverse events will be described in tables including causality, CTCAEgrade, outcome and seriousness. A comparison of specific serious adverse events between the treatment groups (aspirin vs no aspirin and low PPI vs high PPI) will be assessed by examination of 95% confidence intervals for the difference in incidence. An overall category for any serious adverse event will also be compared using the chi square test. The analysis will be conducted by intention to treat. An overall category for renal impairment (dehydration, renal, obstruction) will be compared using the chi square test.

SAE and death major bleeds will be summed and expressed as number of major bleeds per 1000 person years. 2 major bleeds per 10000 person years is expected.

12. Data from Canada

One site in Canada ran a trial of 50 patients using the same protocol. The entire analysis plan will be re-run including this data when it is available.

AspECT

A phase III randomised study of Aspirin and Esomeprazole chemoprevention in Barrett's metaplasia

Funded by CR-UK, MRC, UHL and NCI

ISRCTN No.85156844

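### The exploratory epithelial-cancer analysis of aspirin uses only the two low-PPI arms without a stated reason, and the colon-cancer question raised about high-dose PPI has no dedicated comparison

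*SAP*

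**What the plan says.** The item appears twice in the SAP: as number 5 of the exploratory uses of the data in section 2.1, and with its analysis near the end of section 9.

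- **Proposition.** Section 2.1 opens it as "Investigation of the hypothesis that aspirin will have a chemopreventive effect on all epithelial cancers". A clause introduced by *however* then says that "high dose PPI therapy may arguably increase colon cancer incidence as gastrin levels increase".
- **Outcome.** "Define outcome as time to epithelial cancer (oesophageal, colorectal, other gi or skin"; these sites are pooled into one endpoint.
- **Population.** "For those randomised to aspirin and low PPI or to no aspirin and low PPI", that is, arms A and C.
- **Model.** "use an AFT model with stratification variables to assess if aspirin is predicting outcome". No PPI term and no PPI contrast are specified.

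Two other parts of the SAP come close:

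- The exploratory aim on colorectal adenoma and cancer (section 9): "Using a logrank test, consider if aspirin use is prognostic". It is not restricted by PPI dose, but it tests aspirin only.
- Section 11: "A comparison of specific serious adverse events between the treatment groups (aspirin vs no aspirin and low PPI vs high PPI", judged from 95% confidence intervals for the difference in incidence. Colon cancer is not named, and recording runs until trial medication is stopped.

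On design, SAP section 2.2 says: "The factorial design is efficient due to each patient contributing to the answer to 2 questions".

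**The concern.** The restriction does not fit the rest of the SAP. Section 7 says that exploratory aims use the intention-to-treat sample and that the aspirin sample excludes only patients in the PPI-only randomisation. Section 9 closes by repeating that these analyses use that sample where possible. Section 8.2 keeps both PPI doses in the aspirin comparison and adds the other treatment to the model. Section 8.6 checks interaction by adding a term, not by dropping arms.

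A PPI effect on cancer would not confound the aspirin comparison, because PPI dose is balanced across the aspirin groups by randomisation. Restricting to low PPI changes what is estimated only if aspirin works differently at the two doses. The plan assumes that it does not (SAP 2.5.3 and 8.2), and Protocol section 1.2 expects independent, additive effects.

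Two things are at stake: precision for the aspirin question, and a possible harm that the SAP names, with a mechanism, but for which it sets out no dedicated analysis.

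**Working it through.** **1. Share of patients used.** SAP 2.5.3 plans 2224 patients, about 556 per arm. The two low-PPI arms hold 2 × 556 = 1112, and 1112/2224 = 50%. Of the 2513 actually recruited, some entered the PPI-only randomisation; their number is not given, and they belong to no aspirin comparison. So *half* means half of the aspirin-randomised patients.

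**2. Reproducing the plan's event count.** Inputs from SAP 2.5.3: hazard ratio 1.5 (control to treatment), 80% power, two-sided 5%. (1.960 + 0.842)² = 7.849.

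- Freedman: 7.849 × [(1.5 + 1)/(1.5 − 1)]² = 7.849 × 25 = 196.2, which matches the stated 196.
- Schoenfeld: 4 × 7.849/(ln 1.5)² = 31.40/0.1644 = 191.

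This is the count for a main effect that uses all four arms, for the primary endpoint. The documents give no event count, effect size or power for epithelial cancer.

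**3. Precision.** With equal allocation, the standard error of the log hazard ratio is about 2/√d for d events, and the standard error of an AFT effect also scales roughly with 1/√d. Going from d/2 to d events multiplies it by 1/√2 = 0.71, a fall of 1 − 1/√2 = 29%. Put the other way, the restricted analysis has a confidence interval about √2 = 1.41 times as wide on the log scale. This result needs no assumed event count, only that the high-PPI arms contribute about as many events as the low-PPI arms.

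**4. Illustrative power.** Assume the primary endpoint's hazard ratio of 1.5 and a range of event counts. Power = Φ(√d × ln 1.5/2 − 1.96).

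| Events in all four arms (assumed) | Low-PPI arms only | All four arms |
|---|---|---|
| 50 | 17% | 30% |
| 100 | 30% | 53% |
| 150 | 42% | 70% |
| 196 | 52% | 81% |
| 300 | 70% | 94% |

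For example, at 196 events √196 × 0.4055/2 = 2.84 and Φ(0.88) = 81%; at 98 events √98 × 0.4055/2 = 2.01 and Φ(0.05) = 52%. The rows show what halving the events does. They do not estimate the power of this analysis.

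**5. The gain depends on the model.** Suppose the all-arm model contains aspirin, PPI dose and their interaction, with indicator coding and low PPI as reference. The aspirin coefficient is then the effect within low PPI. At 196 events in all, its standard error is about 2/√98 = 0.20, as in the restricted analysis, so nothing is gained. With main effects only it is 2/√196 = 0.14. The interaction itself is a difference of two such effects, with standard error √(0.20² + 0.20²) = 0.29 (unrounded inputs), twice that of the main effect. This agrees with the SAP's remark in section 8.6 that its interaction test has low power.

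**6. Is high v low PPI for colon cancer covered elsewhere?**

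- Section 9, colorectal aim: aspirin only.
- Section 9, epithelial-cancer item: low-PPI arms only, so it cannot compare doses.
- Section 2.1, exploratory use 6 (dose and time response for esomeprazole): section 9 gives it no outcome or method.
- Section 11: incidence of specific serious adverse events by PPI dose. Serious colon cancers could appear here. However, it is not a time-to-event analysis, and Protocol section 10 does not require reports of most events more than 30 days after trial medication stops.

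**The case against.** The strongest defence is that the item is at heart an aspirin hypothesis. The PPI clause is subordinate, and its *however* may be the reason for the restriction: to estimate the aspirin effect where a suspected opposing influence is absent. That is a coherent target, and a reader need not take the clause as a second formal hypothesis. This stands as far as it goes, but the SAP never states the reason, and avoiding confounding does not require the restriction.

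Several stronger readings are tempting and are not supported:

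- *The PPI harm is never examined.* Section 11 compares serious adverse events by PPI dose and could capture some colon cancers. What is missing is a dedicated analysis.
- *Half the trial is lost for aspirin and colorectal cancer.* The colorectal logrank test carries no PPI restriction; only the pooled epithelial endpoint does.
- *A PPI comparison could use all 2513 patients.* Section 9 ties its other cancer models to data from the time of the new tumour questions, so tumour data may not span the whole trial. Sections 6.3 and 6.6 describe flagging for conversion to cancer, Barrett's adenocarcinoma and death, and do not say that it supplies colorectal cancers.
- *The aspirin estimate is biased.* Nothing in the documents shows that; the low-PPI comparison is itself randomised.

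The item is also exploratory, and under section 10 any later PPI comparison would be labelled exploratory too.

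**Conclusion.** The point holds as a minor one. Without a stated reason, the plan leaves about half of the aspirin-randomised patients out of the epithelial-cancer analysis, against its own factorial logic and sample definition. Using all arms with main effects would cut the standard error of the aspirin effect by about 29%, provided that events roughly double and that aspirin acts similarly at both PPI doses. Nothing firmer can be said about power, because the event count is unknown.

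Separately, the SAP raises a possible increase in colon cancer with high-dose PPI and specifies no dedicated comparison for it. The primary and secondary conclusions are not affected by either part.

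**What to change.** 1. Make the headline analysis an AFT model in all aspirin-randomised patients, with main effects for aspirin and PPI dose plus the stratification variables.
2. Test the aspirin-by-PPI interaction in a separate model, as section 8.6 does for the primary endpoint, and note its low power.
3. Keep the low-PPI result as a sensitivity analysis.
4. Add an exploratory high v low PPI comparison of time to colorectal cancer in all randomised patients with tumour data, and state the period that those data cover.

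The cost is SAP wording and one or two extra models. Time to colorectal cancer or adenoma is already to be derived for the aspirin aim, though the completeness of the tumour data needs checking first. The downside is that the all-arm estimate averages over PPI dose if there is an interaction; the low-PPI sensitivity analysis lets a reader see that.

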9.1 Resource Use and Cost Data

The health economics data for this trial will not be analysed by CSM; the analysis will be undertaken by [name].

10. Exploratory analyses not specified prior to receiving data

Any analyses not specified in this document will be exploratory in nature.

11. Serious adverse events

Serious adverse events are defined as those that are fatal, life threatening, disabling, a congenital birth defect, another important medical event which require hospitalisation or prolongation of hospitalisation. Any serious adverse event occurring whilst a participant is continuing in the study, until trial medication is stopped will be recorded. All serious adverse events will be described in tables including causality, CTCAEgrade, outcome and seriousness. A comparison of specific serious adverse events between the treatment groups (aspirin vs no aspirin and low PPI vs high PPI) will be assessed by examination of 95% confidence intervals for the difference in incidence. An overall category for any serious adverse event will also be compared using the chi square test. The analysis will be conducted by intention to treat. An overall category for renal impairment (dehydration, renal, obstruction) will be compared using the chi square test.

SAE and death major bleeds will be summed and expressed as number of major bleeds per 1000 person years. 2 major bleeds per 10000 person years is expected.

12. Data from Canada

One site in Canada ran a trial of 50 patients using the same protocol. The entire analysis plan will be re-run including this data when it is available.

AspECT

A phase III randomised study of Aspirin and Esomeprazole chemoprevention in Barrett's metaplasia

Funded by CR-UK, MRC, UHL and NCI

ISRCTN No.85156844

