Duration on study:		Participants will be in the study for approximately 8 years or 10 years (if they re-consented to extend) from randomisation to last protocol visit. Follow up will end when the participant either reaches their 8 th (or 10 th if they re-consented) anniversary on trial, choose to withdraw consent, end treatment or on 28 th February 2017 (+3 months for appointment slippage); whichever is soonest.
Study Procedures and frequency:  (Procedures For Remainder of Study)		
Follow Up
 
Patients will be asked questions and their medical notes checked to determine disease, survival and osteoporosis status. Any unreported SAEs, concomitant medications taken and use of other medications/interventions to treat Barrett's will also be determined and noted.
 
Frequency: Annually whilst on study.
 
Endoscopy & Biopsy
 
Endoscopy will be performed on patients to assess their Barrett's status. Biopsy samples will also be taken for local pathology assessment and the Trial Laboratory.
 
Frequency: Year 6, 8 and 10 (if patients re-consented)
 
Blood Samples
 
Blood samples will be taken for the Trial Laboratory to assess for cancer and cardiovascular risk factors.
 
Frequency: Between year 4 and 6 (once), 8 and 10 (if patients re-consented).

Patient care post-trial:		Following the end of study visit patients will receive standard care.
Pharmacokinetic assays:		N/A
Pharmacodynamic assays:		N/A
No. of Study Site(s)		85 Centres in the UK
End of study		Last Patient Last Visit Date is 28 th February 2017 (we will allow +3 months for appointment slippage). Patients should be on the study for a maximum of 123 months.
Publication policy		The results of this study will be published in a peer-reviewed scientific journal and other academic research purposes as agreed by the Investigators.

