## 5.2 Duration of patient participation

Participants will be in the study for approximately 8 years or 10 years (if they re-consented to extend) from randomisation to last protocol visit. Follow up will end when the participant either reaches their 8th (or 10th if they re-consented) anniversary on trial, choose to withdraw consent completely, end treatment or on 28th February 2017 (+ 3 months); whichever is soonest.

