# 6 EARLY PATIENT WITHDRAWAL

## 6.1 Withdrawal from treatment

At any time during the course of the trial, a patient may withdraw early from treatment. The Investigator also has the right to withdraw patients from the study or study treatments if he/she feels that it is in the best interests of the patient. This may happen for a number of reasons, including:

- Unacceptable toxicity
- AE/SAEs requiring discontinuation
- Clinical decision
- Patient decision

When the patient stops treatment early, an 'End of Treatment' Form must be completed along with any other relevant forms, e.g. SAE Form or Consent Withdrawal Notification Form if the patient has withdrawn consent from the whole study. In this case a Consent Withdrawal Form should be offered to the patient to sign (see section 6.3. below). The reason for withdrawing from treatment early should be clearly documented on the End of Treatment form. The patient should continue to be followed-up as per protocol.

At the end of trial participation, all patients must have an End of Treatment Form completed, recording whether they complete treatment as per protocol or withdrew from treatment early.

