### **10 ASSESSMENT OF SAFETY**

The Investigator must monitor each patient for clinical and laboratory evidence of adverse events at each contact with the participant throughout the study. During the course of the annual Follow Up, all patients should be asked directly if they have had any hospital admissions or events which should be reported as a SAE (see definition in Section 10.1). Their patient notes should also be checked for such occurrences. All SAEs should be reported to the Trial Office as described in Section 10.4.

Adverse event monitoring starts from the time the patient commences study medication until they complete the trial. An SAE which occurs more than 30 days after a patient has stopped taking trial medication is not required to be reported, unless the event is related to a trial procedure (e.g. biopsy or blood collection). All SAEs will be followed to a satisfactory conclusion. Any SAEs that are unresolved at the patient's last visit in the study are followed up by the Investigator for as long as medically indicated.

All SAEs reported to the Trial Office will be processed according to internal SOPs. The Trial Office may request additional information for any SAE as judged necessary.

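### SAP section 11 compares any SAE and renal impairment by chi-square with no time at risk, although SAE recording ends when trial medication stops; the likely bias is small and its size unknown

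*SAP*

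**What the plan says.** SAP section 11 sets the SAE recording period as time in the study "until trial medication is stopped will be recorded". The analysis is by intention to treat, so the denominator is everyone randomised to each side of the comparison. On any SAE it says: "An overall category for any serious adverse event will also be compared using the chi square test". Renal impairment is tested in the same way. Specific SAEs get 95% confidence intervals for a difference in incidence, and incidence is not defined. Only major bleeds are "expressed as number of major bleeds per 1000 person years", and the SAP does not say whether those person-years are recorded time or total follow-up.

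Protocol section 10 draws the window differently: "An SAE which occurs more than 30 days after a patient has stopped taking trial medication is not required to be reported", with an exception for events related to a trial procedure. The same section also has adverse event monitoring run until the patient completes the trial. Neither document says whether stopping means one drug or both.

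SAP sections 6.4 and 8.8 describe compliance, withdrawal rates and dose over time. Nothing carries that information into the SAE comparison.

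**The concern.** The numerator is limited by time on trial medication and the denominator is not. With equal true SAE rates, an arm whose patients stop earlier has fewer recorded SAEs because it is watched for less time. The two chi-square tests then partly compare recording time.

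Unequal stopping is plausible. The trial is open-label (SAP 2.6.2), and the protocol's rules for ceasing aspirin (sections 8.4, 8.5 and 8.9) concern aspirin alone. The SAP recognises the issue elsewhere: it uses person-years for bleeds, and in section 9 it notes that the cancer-stage tables ignore differing follow-up. Section 11 has no such note. At stake is the reading of the overall SAE and renal comparisons in an 8 to 10 year trial.

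**Working it through.** **Inputs.** The plan states no figure for these comparisons, so there is none to reproduce. The nearest planning figures, in protocol 13.2, are 20% non-compliance and under 5% side effects on aspirin 300mg. Neither is a stopping rate. All of the following are therefore assumptions:

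- SAE rate r: 3, 6 or 10 per 100 person-years; renal impairment 0.5.
- Treatment period 8.5 years, within the planned 8 to 10.
- 1130 patients per group.
- Share s stopping all trial medication: 20% in one arm and 25%, 30% or 40% in the other.
- Stopping at a constant hazard, unrelated to SAEs.

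**Formulae.** Stopping hazard l = −ln(1 − s)/8.5. Probability of a recorded SAE P = r/(r + l) × [1 − exp(−(r + l) × 8.5)]. z is the pooled two-proportion statistic.

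**Worked case, r = 0.06, equal true rates.**

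- s = 20%: l = 0.02625, so P = 0.06/0.08625 × [1 − exp(−0.7332)] = 0.3615.
- s = 25%: l = 0.03384, so P = 0.06/0.09384 × [1 − exp(−0.7977)] = 0.3514.
- Risk ratio = 0.3514/0.3615 = 0.97. z = −0.0101/√(2 × 0.3565 × 0.6435/1130) = −0.50.

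**All cases (risk ratio, z), no true difference.**

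| Rate per 100 person-years | 20% v 25% | 20% v 30% | 20% v 40% | Share at which z = −1.96, against 20% |
|---|---|---|---|---|
| 0.5 (renal) | 0.97, −0.14 | 0.94, −0.29 | 0.875, −0.61 | 73% |
| 3 | 0.97, −0.35 | 0.94, −0.71 | 0.88, −1.49 | 46% |
| 6 | 0.97, −0.50 | 0.94, −1.01 | 0.88, −2.10 | 39% |
| 10 | 0.97, −0.65 | 0.95, −1.31 | 0.89, −2.70 | 35% |

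**Sensitivity.**

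- With 1256 per side (2513/2, the PPI comparison), z at 20% v 25% is −0.37, −0.53 and −0.68 for 3, 6 and 10 per 100.
- Stopping spread uniformly over 8 years gives a risk ratio of 0.972 to 0.976 for eight-year SAE risks from 1% to 50%. Under that model, with 1256 per side and 30–50% risk, the chance of a false result favouring the earlier-stopping arm is about 6–8%, against a nominal 2.5%.
- If every stopper stopped at once, the ratio would be 0.94.
- Using the protocol's 30-day window changes the ratio by about 0.001.

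**True 15% excess in the earlier-stopping arm, r = 0.06.** Chi-square z is 1.99 with equal 20% stopping, and 1.45, 0.90 and −0.27 with 25%, 30% and 40%. A rate ratio on recorded time, z = ln(1.15)/√(1/d0 + 1/d1) with d = 1130 × P, gives 2.05, 2.04, 2.02 and 1.99. These falls assume that the extra stopping is unrelated to SAEs. If it all follows SAEs, the chi-square z stays at 1.99, because each such patient is already a case.

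**Major bleeds.** The SAP says "2 major bleeds per 10000 person years is expected". Mean recorded time at 20% stopping is 0.20/0.02625 = 7.62 years, so 0.0002 × 1130 × 7.62 = 1.7 bleeds are expected per group. Counting non-fatal bleeds only to stopping but dividing by total follow-up would give null rate ratios of 0.97, 0.94 and 0.87 (7.39, 7.15 and 6.66 years over 7.62). At 1.7 bleeds this is a matter of definition only.

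**The case against.** The strongest reply is that the effect is negligible at any gap the documents suggest. At 6 per 100 person-years the recorded any-SAE proportion moves from 36.1% to 35.1%, and for renal impairment z is −0.14. That stands.

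A reader might infer from the worked figures that a real 15% excess would be lost, z falling from 1.99 to 1.45. The documents do not support that as the expected outcome. Protocol 6.1 lists adverse events requiring discontinuation among the reasons for stopping, and a patient who stops because of an SAE is already in the any-SAE count. The fall applies only to stopping unrelated to SAEs. The reply is weaker for renal impairment, where stopping after a different SAE can still hide a later renal event.

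A reader might also infer that SAEs after stopping are certainly missing. Protocol section 10 does not require reports beyond 30 days, but neither does it bar them, and section 5.1 has sites ask about admissions and check records every year. Later SAEs may be in the database.

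Nor is the aspirin comparison safe merely because a patient who stops only aspirin may stay on esomeprazole. The bias is absent only if stopping means all trial medication and esomeprazole stopping is equal with and without aspirin. Neither is stated.

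Dose step-downs (protocol 8.5) may narrow any gap in stopping, and SAP 6.4 and 8.8 would let a reader notice one. Both points are fair, but neither adjusts the comparison.

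**Conclusion.** The concern holds, at low priority. SAP section 11 pairs a numerator limited by time on medication with a denominator of all randomised patients, and makes no allowance for time at risk in the any-SAE and renal comparisons. Specific SAEs share the problem only if incidence means a proportion.

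Direction and size cannot be known from the documents. At an assumed 20% v 25% stopping the bias is about 3%, and the expected z reaches −1.96 only at about 20% v 35–46% (73% for renal impairment). For any SAE these figures are an upper bound as to the reason for stopping, since stopping that follows an SAE adds no bias. They are not a bound as to timing, because very early stopping would raise the bias. The material does not show that the safety conclusions would be wrong.

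The protocol also conflicts with itself on whether follow-up continues once treatment ends: section 5.2 ends it at the soonest of several events including the end of treatment, while 6.1 says "The patient should continue to be followed-up as per protocol". That affects all endpoints and should be raised separately.

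**What to change.** In SAP section 11:

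1. Reconcile the SAE window with protocol section 10 (30 days after stopping, and monitoring to trial completion). State whether stopping means either drug or both, and whether a permitted break closes the window.
2. Beside the planned chi-square tests, report any SAE (first event), renal impairment and specific SAEs as rates per person-year in the recorded window, with rate ratios and 95% confidence intervals. Use the same denominator for major bleeds.
3. Show time on trial medication by arm next to the SAE table, building on SAP 6.4 and 8.8. State that rates do not remove bias from stopping that is related to SAE risk.
4. If SAEs after stopping are in the database, add a sensitivity analysis that includes them.

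The cost is some SAP wording and an exposure derivation from End of Treatment forms and pharmacy logs, with Change of Treatment forms if breaks count. Appendix 1 already needs pharmacy data for the per-protocol sample, but only for the first year. SAP 6.4 assumes compliance from prescription collection and visit attendance, so exposure will be approximate. Nothing planned is lost, but bias from informative stopping remains. Version 2.0 is dated 24 August 2017 and the final analysis was due to start in September 2017, so a later change should be described and justified as the SAP introduction requires.
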